6.5 Product Use Instructions

Participants will receive study product use instructions at the Enrollment Visit and at additional follow-up visits, as needed. Site staff will counsel participants in VR product use; including, to refrain from removing the ring (except as directed), and instructions for re-insertion in case of accidental ring expulsion, etc. Additional details will be provided in the MTN-024/IPM 031 SSP Manual. Participants will also be counseled on prohibited practices as described in Section 6.7.

6.6 Concomitant Medications

Enrolled study participants may use concomitant medications during study participation with the exception of medications and products listed as prohibited. All concomitant medications as well as illicit substances reported throughout the course of the study will be recorded on case report forms (CRFs) designated for that purpose. All prescription

medications, over-the-counter preparations, vitamins, nutritional supplements, and herbal preparations will be recorded on forms for concomitant medications.

Concomitant medications that either inhibit or induce CYP450 enzymes will be permitted. Systemic exposure to dapivirine observed in women following use of dapivirine ring is very low. Therefore, there is not expected to be a significant change in the dapivirine concentration with concomitant use of CYP450 (including CYP3A4) inducers or inhibitors. The low systemic exposure to dapivirine also suggests that it is very unlikely to induce the metabolism of other co-administered drugs.

6.7 Use of Intravaginal Medications/Products and Practices

All participants will be counseled to avoid the use of non-study vaginal products during study participation. Concomitant use of prohibited non-study vaginal products or other devices including, but not limited to: spermicides, female condoms, diaphragms, topical or systemic hormone replacement treatment, including vaginal estrogens, and/or hormonal contraceptives, vaginal medications, menstrual cups, cervical caps (or any other vaginal barrier method), vaginal douches, lubricants and moisturizers, sex toys (vibrators, dildos, etc.) will be assessed. These products will be recorded on forms designed for that purpose. Participants who report use of these products during study product use periods will be counseled regarding the use of alternative methods and study staff should reference Section 9.3 and 9.4 for temporary hold and/or permanent discontinuation guidelines. Condoms provided by study staff will not be coated with any type of spermicide.

Use of study approved lubricant is permitted, however, participants should abstain from inserting anything into the vagina for 72 hours prior to each clinic visit, including abstaining from the use of study approved lubricant and vaginal intercourse. Participant use of these products, including frequency and amount of study-approved lubricant used, when available, and sexual intercourse will be assessed at each follow-up visit. Visits need not be rescheduled in the event that a participant reports the use of vaginal products or engaging in a coital episode in the previous 72 hours, see the MTN-024/IPM 031 SSP Manual available at www.mtnstopshiv.org.

In addition, participants in the Intensive PK subset should refrain from engaging in vaginal intercourse for 72 hours following the collection of the biopsies.

7 STUDY PROCEDURES

An overview of the study visit and evaluations schedule is provided in Appendix I. Presented in this section is additional information on visit-specific study procedures. Detailed instructions to guide and standardize procedures across sites are provided in the MTN-024/IPM 031 SSP Manual available at www.mtnstopshiv.org.

Figure 1: Study Visit Schedule

7.1 Pre-screening

As part of participant outreach and recruitment strategies, study staff may pre-screen potential study participants at either on-site or off-site locations. During these interactions, study staff may explain the study to potential participants and ascertain elements of presumptive eligibility, to be confirmed at an on-site screening visit. Process information (e.g., number of potential participants contacted, number presumptively eligible) may be recorded and stored at the study site in the absence of written informed consent from potential participants, provided the information is collected in such a manner that it cannot be linked to participant identifiers. At each site, procedures and documentation will comply with local IRB requirements.

7.2 Screening Visit

A Screening Visit may take place up to 45 days prior to the Enrollment Visit. Multiple visits may be conducted to complete all required screening procedures, if necessary. Written informed participant consent will be obtained at the Screening Visit before any screening procedures are initiated. For participants who do not meet the eligibility criteria, screening will be discontinued once ineligibility is determined.

Table 4: Screening Visit

Screening Visit		
Component	Procedures	
Administrative and Regulatory	
 ● Obtain written informed consent for Screening, Enrollment and Long-Term Storage and Future Testing ● Assign participant identification (PTID) ● Collect locator information ● Collect demographic information ● Assess eligibility ● Provide reimbursement ● Schedule next visit* 	
Behavioral/Counseling	
 ● Provide counseling 
 ○ HIV/STI risk reduction ○ Male condom ○ HIV pre-and post-test 	
Clinical	
 ● Obtain medical history ● Obtain menstrual history ● Obtain concomitant medications ● Perform physical examination ● Perform pelvic examination ● Disclosure of available test results ● Treat for UTI/RTI/STI or refer* 	
Laboratory	Urine	
 ● Collect urine for: 
 ○ Human chorionic gonadotropin (hCG) ○ Dipstick UA and/or urine culture per local standard of care*
	Blood	
 ● Collect blood for: 
 ○ Serum chemistries ○ Complete blood count (CBC) with platelets ○ HIV-1 serology ○ Syphilis serology ○ Follicle-stimulating hormone (FSH)
	Pelvic Samples	
 ● Pelvic Sample Collection 
 ○ Vaginal swab for rapid Trichomonas test ○ Vaginal nucleic acid amplification test (NAAT) for Neisseria gonorrhoeae and Chlamydia trachomatis (GC/CT) ○ Saline wet mount for BV* ○ Potassium hydroxide (KOH) wet mount for candidiasis* ○ Pap smear interpretation* ○ Herpes lesion testing*
Study Product Supply		
 ● Provide study condoms*

*If indicated

7.3 Enrollment Visit (Day 0)

Table 5: Enrollment Visit

Enrollment Visit		
Component	Procedures	
Administrative and Regulatory	
 ● Review/update locator information ● Confirm eligibility ● Randomization ● Provide reimbursement ● Schedule next visit and/or contact 	
Behavioral/Counseling	
 ● Administer baseline behavioral assessment ● Administer product preference/acceptability assessment ● Provide counseling 
 ○ HIV/STI risk reduction ○ Product adherence ○ Protocol adherence ○ HIV pre and post-test* ○ Male condom* 	
Clinical	
 ● Review medical history, to include: 
 ○ Menopausal Rating Scale ○ Urogenital Distress Inventory (UDI-6 Short Form) ● Review/update concomitant medications ● Perform physical examination ● Perform pelvic examination 
 – Visual inspection per guidelines for naked eye inspection described in the World Health Organization (WHO)/CONRAD Manual for Standardization of Colposcopy for the Evaluation of Vaginal Products, Update 2004 ● Disclosure of available test results ● Treat for UTIs/RTIs/STIs or refer* 	
Laboratory	Urine	
 ● Collect urine for: 
 ○ hCG* ○ Dipstick UA and/or urine culture, per local standard of care*
	Blood	
 ● Collect blood for: 
 ○ Plasma archive ○ HIV-1 serology* ○ Serum chemistries* ○ CBC with platelets*
	Pelvic Samples	
 ● Pelvic Sample Collection 
 ○ Vaginal swab for Gram stain ○ Vaginal pH ○ Vaginal swab for quantitative vaginal culture ○ Cytobrush for flow cytometry Θ ○ Cervicovaginal lavage (CVL) for biomarkers ○ Vaginal swabs for biomarkers ○ Vaginal NAAT GC/CT* ○ Saline wet mount for BV* ○ KOH wet mount for candidiasis* ○ Vaginal swab for rapid Trichomonas test* ○ Herpes lesion testing*

Enrollment Visit	
Component	Procedures
Study Product Supply	
 Participants will receive study VR, product use instructions and will be instructed to self-insert the study VR, followed by bimanual exam to check placement Provide male condoms* Provide lubricant*

* If indicated, Θ To be collected on participants with appropriate anatomy at selected site(s)
Note: Cervical samples will be collected on women with appropriate anatomy.

7.4 Follow-up Study Visits and Phone Calls

Table 6: 4-Week and 8-Week Study Visits

4-Week and 8-Week Study Visits		
Component	Procedures	
Administrative and Regulatory	
 Review/update locator information Provide reimbursement Schedule next study visit 	
Behavioral/Counseling	
 Administer behavioral assessment Administer adherence assessment Administer product preference/acceptability assessment Provide counseling 
 HIV/STI risk reduction Product adherence Protocol adherence HIV pre-and post-test* Male condom* 	
Clinical	
 Obtain medical history, to include: 
 Urogenital Distress Inventory (UDI-6 Short Form) Review/update concomitant medications Perform targeted physical examination Perform pelvic examination 
 Visual inspection per guidelines for naked eye inspection described in the WHO/CONRAD Manual for Standardization of Colposcopy for the Evaluation of Vaginal Products, Update 2004 Record/update AEs Disclosure of available test results Treat for UTIs/RTIs/STIs or refer* 	
Laboratory	Urine	
 Collect urine for: 
 Dipstick UA and/or urine culture, per local standard of care* NAAT for GC/CT*
	Blood	
 Collect blood for: 
 PK HIV-1 serology* Serum chemistries* CBC with platelets*
	Samples	
 Pelvic Sample Collection 
 CVL for biomarkers (at 4-week only) Vaginal swabs for biomarkers (at 4-week only) Vaginal swab for Gram stain Vaginal swab for quantitative vaginal culture Tear test strips for PK on a subset of participants (See Section 7.7) Vaginal pH Saline wet mount for BV* KOH wet mount for candidiasis* Vaginal swab for rapid Trichomonas test* Herpes lesion testing*

4-Week and 8-Week Study Visits	
Component	Procedures
Study Product Supply	
 ● Participants will receive study VR, product use instructions and will be instructed to self-insert the study VR, followed by bimanual exam to check placement ● Collect study product ● Provide male condoms* ● Provide lubricant*

* If indicated

Table 7: 12-Week Final Clinic Visit/ Early Termination Visit

12-Week Final Clinic Visit/ Early Termination Visit		
Component	Procedures	
Administrative and Regulatory	
 ● Review/update locator information ● Provide reimbursement ● Schedule next contact 	
Behavioral/Counseling	
 ● Administer behavioral assessment ● Administer adherence assessment ● Administer product preference/acceptability assessment ● In-depth interview on a subset of participants (See Section 7.8) ● Provide counseling 
 ○ HIV pre-and post-test ○ HIV/STI risk reduction ○ Male condom* 	
Clinical	
 ● Review/update medical history, to include: 
 ○ Menopause Rating Scale ○ Urogenital Distress Inventory (UDI-6 Short Form) ● Review/update concomitant medications ● Perform targeted physical examination ● Perform pelvic examination 
 ○ Visual inspection per guidelines for naked eye inspection described in the WHO/CONRAD Manual for Standardization of Colposcopy for the Evaluation of Vaginal Products, Update 2004 ● Record/update AEs ● Disclosure of available test results ● Treat for UTIs/RTIs/STIs or refer* 	
Laboratory	Urine	
 ● Collect urine for: 
 ○ NAAT for GC/CT* ○ Dipstick UA and/or urine culture, per local standard of care*
	Blood	
 ● Collect blood for: 
 ○ PK ○ Serum chemistries ○ CBC with platelets ○ HIV-1 serology

12-Week Final Clinic Visit/ Early Termination Visit	
Component	Procedures
Pelvic Samples	
 ● Pelvic Sample Collection 
 ○ Vaginal swab for Gram stain ○ Vaginal swab for quantitative vaginal culture ○ Tear test strip(s) for PK on a subset of participants (See Section 7.7) ○ Vaginal pH ○ Vaginal swabs for biomarkers ○ Cytobrush for flow cytometry Θ ○ CVL for biomarkers ○ Cervical biopsies for PK on a subset of participants (Intensive PK) (See Section 7.7) ○ Saline wet mount for BV* ○ KOH wet mount for candidiasis* ○ Vaginal swab for rapid Trichomonas test* ○ Herpes lesion testing*
Study Product Supply	
 ● Collect study product ● Provide male condoms*

* If indicated , Θ To be collected on participants with appropriate anatomy at selected site(s)

7.4.1 Follow-Up Phone Calls: 1-Week, and 13-Week/Study Termination

Study staff will follow-up with participants via phone call one week following the Enrollment Visit and one week following the 12-Week Final Clinic Visit/Early Termination Visit. Study staff will inquire about AEs.

Table 8: 1-Week and 13-Week/Study Termination Follow-Up Phone Calls

Component	Procedures
Administrative and Regulatory	
 ● Provide reimbursement~
Clinical	
 ● Concomitant medications ● Record/update AEs

~ Sites to reference SOPs

7.5 Follow-up Procedures for Participants Who either Temporarily or Permanently Discontinue Study Product

Except in the specific cases mentioned below (see Sections 7.5.1 and 7.5.2), a participant who discontinues study product will be encouraged to remain in the study if they are willing.

7.5.1 Participants Who Become Infected with HIV-1

If a participant becomes infected with HIV-1 after the Enrollment Visit, she will be referred to local care and treatment services and may return to the research clinic for additional counseling and other support services, as needed. Follow-up visits will be discontinued and the participant will be considered terminated from the study. Participants who seroconvert after randomization may be offered additional laboratory testing (such as HIV viral load and HIV drug resistance testing), as clinically indicated per discussion between IoR and NL. Please reference the MTN-024/IPM 031 SSP Manual for additional details (www.mtnstopshiv.org).

7.5.2 Participants Who Become Pregnant

This study will be enrolling postmenopausal women, thus it is extremely unlikely that a participant will become pregnant during this study. In the rare event a participant becomes pregnant, she will be referred to local health care services and may return to the research clinic for additional counseling, as needed. Continued study participation would be of no added benefit to the participant, thus follow-up visits and procedures will be discontinued and the participant will be considered terminated from the study.

Participants who become pregnant while on study product may be offered enrollment in MTN-016 (www.mtnstopshiv.org), provided their study site is taking part in MTN-016.

For additional details about obtaining pregnancy outcome, please reference the MTN-024/IPM 031 SSP (www.msnstopshiv.org).

7.5.3 Participants Who Voluntarily Discontinue Study Product

All protocol-specified study procedures will continue except:

- Provision of study product
- PK specimen collection
- Provision of counseling:
 - Adherence
 - Product use
- Pelvic exams, unless required for AE follow-up

The behavioral assessments will be administered according to guidance from the protocol team.

The aforementioned study procedures will occur at the visit that product is discontinued and then be omitted at subsequent visits. Completion of these procedures will resume if/when study product use is restarted.

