10.2 Study Endpoints

Primary endpoints

Consistent with the primary study objective to assess the safety of dapivirine (25 mg) administered in a silicone elastomer vaginal matrix ring, when inserted once every 4 weeks during 12 weeks of study product use by healthy, sexually active, HIV-uninfected postmenopausal females, as compared with a placebo, the primary safety endpoints are the proportion of females in each of the two arms with:

- Evidence of Grade 2 or higher genital, genitourinary and reproductive system AEs as defined by the Division of AIDS Table for Grading the Severity of Adult and Pediatric Adverse Events, Version 1.0, Dec 2004 (Clarification dated August 2009), Addendum 1, (Female Genital Grading Table for Use in Microbicide Studies) judged to be related to study product
- Evidence of Grade 3 or higher AEs as defined by the Division of AIDS Table for Grading the Severity of Adult and Pediatric Adverse Events, Version 1.0, Dec 2004 (Clarification dated August 2009)

Secondary endpoints

Consistent with the secondary study objective to evaluate acceptability of study VR expressed as women's preference for the VR compared to other HIV prevention methods in HIV-uninfected postmenopausal women, the following endpoint will be assessed:

- The proportion of participants who find the study VR to be as acceptable as other HIV prevention methods

Consistent with the secondary study objective to evaluate the adherence to the dapivirine VR versus the placebo VR for 12 weeks of continuous use, the following endpoint will be assessed:

- Adherence measures of daily study product use based on self-report for each participant over the study product use period

Consistent with the secondary study objective to evaluate the systemic and local dapivirine exposure, the following endpoint will be assessed:

- Dapivirine concentrations in plasma, vaginal fluid and cervical tissue

Exploratory Endpoints

Acceptability

- Participant's self-report on multiple components of acceptability via attitudinal questions

Adherence

- Residual amount of dapivirine measured in returned VRs
- Dapivirine concentrations in plasma, vaginal fluid, and cervical tissue

Vaginal Microenvironment

- Changes in pH, microflora and biomarkers

Note: Cervical tissue will be collected on a subset of participants taking part in the Cervical Biopsy/Vaginal Fluid Subsets

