10.5 Participant Accrual, Follow-up and Retention

Based on previous studies of vaginal products, the accrual of 96 eligible participants will take approximately 12 months. Participants lost to follow-up and/or on temporary hold or permanent product discontinuation will not be replaced. However, every effort will be made to complete their regularly scheduled safety evaluations. Additionally, participants who are found to be HIV-infected and/or pregnant after enrollment will be terminated from the study and will not be replaced. Each site will target retention of 95% of enrolled participants over the 13-Week follow-up period.

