10.8.2 Primary Analysis

When the use of descriptive statistics to assess group characteristics or differences is required, the following methods will be used: for categorical variables, the number and percent in each category; for continuous variables, the mean, median, standard deviation, quartiles and range (minimum, maximum). Within-treatment group assessment of the change from the baseline measurement to a follow-up measurement will be analyzed using McNemar's test (for categorical response variables) or the paired t-test or Wilcoxon signed-ranks test (for continuous variables). When use of formal testing to assess differences between users of the placebo VR and users of the dapivirine VR is required, the following methods will be used: for binomial response variables, chi-square tests and logistic regression (or exact testing methods); for continuous variables, t-tests and linear regression or nonparametric methods if data are non-Normal.

To assess the adequacy of the randomization, participants in each of the two arms will be compared for baseline characteristics including demographics and laboratory measurements using descriptive statistics.

Safety Endpoints

All females randomized into the study will be included in the primary analysis according to principle of Intent-to-Treat. To assess safety, the number and the percentages of participants experiencing each safety endpoint will be tabulated by study arm. Each participant will contribute once in each category (i.e., only for the highest severity AE for each participant) for the calculation of event rates. Exact binomial confidence intervals will be calculated for each safety endpoint for each arm and Fisher's exact test used to test for differences in event rates between the two arms.

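### Sections 7.5.3 and 7.5.4 drop scheduled pelvic exams after product discontinuation, against 10.5 and the continued pelvic sampling, so detection of the genital primary endpoint depends partly on staying on product; the likely effect is small

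*Protocol*

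**What the plan says.** Protocol 7.5.3 (voluntary discontinuation) and 7.5.4 (discontinuation by the investigator) use the same rule. It opens with "All protocol-specified study procedures will continue except" and lists, among the exceptions, "Pelvic exams, unless required for AE follow-up". On timing: "The aforementioned study procedures will occur at the visit that product is discontinued and then be omitted at subsequent visits". The procedures resume if product is restarted. Section 7.5 is headed as covering temporary as well as permanent discontinuation.

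Section 10.5 addresses the same women. It says "Participants lost to follow-up and/or on temporary hold or permanent product discontinuation will not be replaced" and continues: "However, every effort will be made to complete their regularly scheduled safety evaluations". Appendix I and Tables 6 and 7 require a pelvic exam with naked-eye inspection at weeks 4, 8 and 12.

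The first primary endpoint in 10.2 is the proportion in each arm with "Evidence of Grade 2 or higher genital, genitourinary and reproductive system AEs", graded by the Female Genital Grading Table and "judged to be related to study product". Section 10.8.2 sets the analysis population: "All females randomized into the study will be included in the primary analysis according to principle of Intent-to-Treat". It tabulates the number and percentage with each endpoint by arm. Section 10.8.4 provides secondary and sensitivity analyses for missing data, including imputation under extreme scenarios. It does not say whether an exam omitted by design counts as missing.

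**The concern.** The omitted procedure is one of the ways the first primary endpoint is measured. Exclusion criterion 5 applies the Female Genital Grading Table to pelvic exam findings observed by staff. Section 9.6 lists signs found by inspection, such as epithelial disruption, erythema, edema, petechiae and ecchymosis. A sign without symptoms cannot trigger the AE follow-up exception, because that exception needs an AE that is already known.

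After the discontinuation visit, the chance of detecting such a sign therefore depends on whether the woman is still using the ring, while she stays in the intent-to-treat denominator. A lost event can only lower the observed rate. If women stop because of genital intolerance and this differs by arm, the arm contrast is affected too.

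**Working it through.** **1. The texts side by side.**

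| Place in the protocol | Woman in follow-up, off product |
|---|---|
| 7.5.3, 7.5.4 | Pelvic exam at the discontinuation visit; later only for AE follow-up |
| 10.5 | Every effort to complete scheduled safety evaluations |
| Appendix I, Tables 6 and 7 | Pelvic exam required at weeks 4, 8 and 12 |
| 7.5.3, 7.5.4 exception list | PK specimens stop; other pelvic samples (pH, Gram stain, culture, CVL, biomarker swabs, cytobrush) are not exempted |
| 7.9 | Refers to specimen collection as done during pelvic exams |
| Table 7 | The week-12 visit doubles as the Early Termination Visit and includes a pelvic exam |

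Two tensions follow. The exam is dropped in one section and promised, as part of scheduled safety evaluations, in another. And the pelvic samples continue while the exam at which they are collected does not. In addition, a woman who leaves the study is due a final exam, whereas one who stays in follow-up off product has none at week 12.

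**2. Number of exams affected.** The protocol gives no product-discontinuation rate; its 95% figure is a study-retention target. Assume 7 of the 72 drug-arm women (9.7%) stop at week 4. They are examined at week 4 and miss weeks 8 and 12.

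- Scheduled drug-arm follow-up exams: 72 × 3 = 216
- Omitted: 7 × 2 = 14
- Share: 14/216 = 6.5%

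**3. Expected number of lost events.** Assume further a true rate of 5%, every event visible only on exam, and events spread evenly over the exams. Expected loss = 72 × 0.05 × 0.065 = 0.23 events.

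**4. What one lost event does.** The Clopper-Pearson limits in Table 11 reproduce: the upper 95% limit is 4.99% for 0/72 and 7.50% for 1/72. Missing a single event would turn the second into the first. This shows how sensitive a low count is; it is not a forecast.

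**5. Effect on Table 12.** Full enumeration of the two-sided Fisher's exact test (24 versus 72, alpha 0.10) at 4.2% versus 26.3% gives power 80.3%, against the stated 80%. At 30.2% it gives 90.2%, against the stated 90%. These figures assume full ascertainment.

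Let d be the fraction who discontinue and s the share of their events visible only at omitted exams. Then observed rate = true rate × (1 − d·s). Both d and s are assumptions.

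| d | s | Observed drug-arm rate | Power, loss in both arms | Power, loss in drug arm only |
|---|---|---|---|---|
| 5% | 0.25 | 26.0% | 79.5% | 79.2% |
| 5% | 0.5 | 25.6% | 78.8% | 78.1% |
| 10% | 0.5 | 25.0% | 77.1% | 75.8% |
| 10% | 1 | 23.7% | 73.6% | 70.6% |
| 20% | 1 | 21.0% | 65.5% | 58.8% |

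The last row needs one woman in five to stop and all of those women's events to be visible only at omitted exams. The protocol does not suggest either condition.

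**The case against.** The case against is substantial, and most of it limits the size of the problem.

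- **Women are still followed.** They are examined at the discontinuation visit and whenever AE follow-up requires it. Medical history (with the UDI-6), targeted physical exam, AE recording and the 13-week call continue, and interim visits are allowed. Symptomatic events are still captured. This stands.
- **Only related events count, and they are expected early.** Section 2.8.2 expects AEs within 5 days of ring removal. After a stop at week 4, the first omitted exam is about 4 weeks later. Completers also have their last exam at ring removal, followed by a phone call. This stands, although the 5-day expectation rests on studies of women aged 18 to 40, and the protocol says that no completed trial covered this age group.
- **Discontinuation may be rare.** In the 12-week, 280-woman trial of this ring (IPM 015, Section 2.6.1), no SAE or TEAE led to premature discontinuation apart from two placebo-arm events. This argues for a low d, again in a different population.
- **Section 10.5 is general wording.** It does not name pelvic exams and could be read as subject to 7.5.3 and 7.5.4. That softens the conflict. It does not remove it, because 10.5 speaks specifically of women on hold or off product and Appendix I schedules the exam.
- **Section 10.8.4 already has the sensitivity analysis.** It does, and further detail may properly sit in an analysis plan that is not shown. But no analysis recovers a finding that the visit procedures never collected.

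A reader might infer that discontinuers are counted as event-free without being examined. The protocol does not support that. They are examined at discontinuation, their earlier and later reported events count, and no scoring rule for omitted exams is stated. A reader might also infer that exam-only findings are a main source of primary events. The protocol does not quantify them, and the ring-associated AEs listed in 13.4.1 are mostly symptomatic.

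**Conclusion.** The inconsistency is real: 7.5.3 and 7.5.4 conflict with 10.5, and with the pelvic sampling they leave in place. Its statistical consequence is narrow. What can be lost is a related, Grade 2 or higher genital sign, without symptoms, first visible after the discontinuation visit. Such a loss understates harm, and it could do so unequally between arms if discontinuation differs by arm; nothing in the protocol shows that it will. No effect on the second primary endpoint (Grade 3 or higher AEs of any kind) is shown.

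The likely size is small. Under the illustrative assumptions, 6.5% of drug-arm exams are omitted and about 0.23 events are lost in expectation. Power falls by roughly one to five percentage points when 5% to 10% of women stop and half or less of their events are visible only on exam. Larger losses need assumptions that the protocol gives no reason to make. The point is still worth correcting, because the trial expects few events and its conclusion is one of safety.

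**What to change.** - **Procedures.** Reconcile 7.5.3 and 7.5.4 with 10.5 and Appendix I by keeping the already scheduled week-12 pelvic exam for women followed off product who agree to it.
- **Analysis.** State that the extreme-case sensitivity analysis in 10.8.4 applies to the genital endpoint for discontinuers with no later exam.

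The cost is a few sentences and one exam per woman off product, so at most 7 in the drug arm in the example above. That visit already calls for pelvic samples that 7.5.3 and 7.5.4 do not exempt. The downside is some added burden for women who have stopped the ring, and some will decline; the sensitivity analysis covers those who do.
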